9.1.3.2. Modified Intention-To-Treat (mITT) Population

All randomized subjects analyzed according to their randomized treatment. Subjects who meet the anti-hypertensive medication escape criteria (office SBP ≥ 180 mmHg or < 115 mmHg associated with symptoms of hypotension or safety concern requiring medication changes) will be excluded from this population. Office and ambulatory blood pressure outcomes out to 6 months follow-up will be presented for this population.

9.1.3.3. Per Protocol Population

All randomized subjects, meeting the following criteria:

1. Subjects showing medication compliance in blood and/or urine (via drug testing data) at SV2, 3-months, and 6-months, compared with prescribed AH Meds at SV2.
2. Exclude subjects with protocol deviation code 101 (consent not obtained).
3. Exclude subjects who do not meet the following Inclusion/Exclusion criteria:
 - Inclusion: Individual has an office SBP ≥ 150 mmHg and < 180 mmHg and an office DBP ≥ 90 mmHg measured at SV2, according to the guidelines in Appendix L7 of the study protocol.

- Inclusion: Individual has a 24-hour ABPM average SBP ≥ 140 and < 170 mmHg measured at SV2, according to guidelines in Appendix L7 of the study protocol.
 - Exclusion: Individual has undergone prior renal denervation.
 - Exclusion: Individual has renal artery anatomy that is ineligible for treatment.
4. Exclude subjects meeting the anti-hypertensive medication escape criteria (office SBP ≥ 180 mmHg OR < 115 mmHg associated with symptoms of hypotension or safety concern requiring medication changes).
 5. Exclude subjects who did not receive the treatment they were randomized to.

Office and ambulatory blood pressure outcomes out to 6 months follow-up will be presented for this population.

9.1.3.4. Medication Adherence Population 1

All randomized subjects, meeting the following criteria:

1. Subjects showing medication compliance in blood and/or urine (via drug testing data) at SV2, 3-months, and 6-months, compared with prescribed AH Meds at SV2.
2. Exclude subjects meeting the anti-hypertensive medication escape criteria (office SBP ≥ 180 mmHg OR < 115 mmHg associated with symptoms of hypotension or safety concern requiring medication changes).
3. Exclude subjects who did not receive the treatment they were randomized to.

Office and ambulatory blood pressure outcomes out to 6 months follow-up will be presented for this population.

9.1.3.5. Medication Adherence Population 2

All randomized subjects, meeting the following criteria:

1. Subjects showing medication compliance in blood and/or urine (via drug testing data) at 3-months and 6-months, compared with drug testing AH Meds at SV2.
2. Exclude subjects meeting the anti-hypertensive medication escape criteria (office SBP ≥ 180 mmHg OR < 115 mmHg associated with symptoms of hypotension or safety concern requiring medication changes).
3. Exclude subjects who did not receive the treatment they were randomized to.

Office and ambulatory blood pressure outcomes out to 6 months follow-up will be presented for this population.

9.1.3.6. Medication Adherence Population 3

All randomized subjects, meeting the following criteria:

1. Subjects showing medication compliance in blood and/or urine (via drug testing data) at 3-months and 6-months, compared with drug testing AH Meds at SV2. If a subject is compliant at 3M, but not compliant at 6M, then their 3M BP will be used at 6M.
2. Exclude subjects meeting the anti-hypertensive medication escape criteria (office SBP ≥ 180 mmHg OR < 115 mmHg associated with symptoms of hypotension or safety concern requiring medication changes).
3. Exclude subjects who did not receive the treatment they were randomized to.

Office and ambulatory blood pressure outcomes out to 6 months follow-up will be presented for this population.

9.1.3.7. As Treated Population

All randomized subjects, analyzed according to the actual treatment received. Subjects randomized to RDN who do not get treated will be analyzed in the control arm. Subjects who meet the anti-hypertensive medication escape criteria (SBP \geq 180 mmHg or safety reasons requiring medication changes) will be analyzed using Last Observation Carried Forward (LOCF) for their blood pressure measurements. Office and ambulatory blood pressure outcomes out to 6 months will be presented for this population.

9.1.4. Crossover Procedures

Control subjects may crossover to receive renal denervation therapy after completing their 6 month follow-up visit. For the subjects who have already completed their 6-month visit at the time crossover procedures are available per protocol, the decision to crossover must take place at their next in-person visit (6, 12, 24 and 36-month follow-up or Unscheduled visit). All subjects will have 30 days from that visit to undergo the crossover procedure. Subjects that are more than 30 days from 6, 12, 24 or 36-month or unscheduled visit, must complete a crossover baseline visit prior to having the crossover renal denervation procedure. To crossover, the required baseline data must be collected, and the subject cannot meet any of the anatomical or eGFR exclusion criteria. Crossover subjects will undergo follow up visits at 1, 3, 6, 12, 24, and 36 months post-procedure. Subjects who do not meet required eligibility for crossover on the day of the procedure will undergo follow-up visits according to their original follow-up schedule. Crossover procedures will be offered once and will not be available at a later time if it was declined by the control subject during the allowed 30-day window.

9.2. General Methodology

Descriptive statistics of continuous outcomes will be presented by treatment group and include sample size, mean, median, standard deviation, minimum and maximum. For categorical outcomes, the number and percentage of subjects in each category will be presented by treatment group. Statistical comparisons between treatment groups will be made using the independent samples t-test for continuous outcomes and Fisher's exact test for categorical outcomes. Paired t-tests will be used to compare changes in blood pressure from baseline to follow-up within each treatment group. All statistical analyses will be performed using SAS for Windows (version 9.2 or higher) or other widely accepted statistical or graphical software. Patient data listings and tabular and graphical presentations of results will be provided. Unless otherwise specified, a two-sided 0.05 level of significance will be used to declare treatment groups significantly different.

9.3. Poolability Analyses

9.3.1. Poolability of study centers

The following analyses will be performed to evaluate the poolability of data from different study centers. If the resulting tests are significant at the 0.15 level, further exploratory analysis will be attempted to identify covariates that may explain differences. Otherwise, the data will be considered to be poolable across study centers.

- A logistic regression will be conducted, with Major Adverse Events (MAE) as the dependent variable, and treatment, study center, treatment * study centers as independent variables. If the interaction term is not significant at 0.15 level, then the treatment effect in the primary safety endpoint is considered consistent among the sites.
- A linear regression will be conducted, with change in SBP from baseline to 6 months as measured by 24-hour ABPM as the dependent variable, and baseline systolic ABPM, treatment, study center, treatment * study center interaction term as independent variables. If the interaction term is not significant at 0.15 level, then the treatment effect in the primary effectiveness endpoint is considered consistent among the study centers.

9.3.2. Poolability of US and Canada

The following analyses will be performed to evaluate the poolability of data from US and Canadian sites. If the resulting tests are significant at the 0.15 level, further exploratory analysis will be attempted to identify covariates that may explain differences. Otherwise, the data will be considered to be poolable across regions.

- A logistic regression will be conducted, with MAE as the dependent variable, and treatment, US/Canada, treatment * US/Canada as independent variables. If the interaction term is not significant at 0.15 level, then the treatment effect in the primary safety endpoint is considered consistent between US and Canadian regions.
- A linear regression will be conducted, with change in SBP from baseline to 6 months as measured by 24-hour ABPM as the dependent variable, and baseline systolic ABPM, treatment, US/Canada, treatment * US/Canada interaction term as independent variables. If the interaction term is not significant at 0.15 level, then the treatment effect in the primary effectiveness endpoint is considered consistent between US and Canadian regions.

9.3.3. Poolability of North America (US and Canada)/Rest of World (ROW)

The following analyses will be performed to evaluate the poolability of data from North America (NA) and Rest of World (ROW) sites. If the resulting tests are significant at the 0.15 level, further exploratory analysis will be attempted to identify covariates that may explain differences. Otherwise, the data will be considered to be poolable across regions.

- A logistic regression will be conducted, with MAE as the dependent variable, and treatment, NA/ROW, treatment * NA/ROW as independent variables. If the interaction term is not significant at 0.15 level, then the treatment effect in the primary safety endpoint is considered consistent between NA and ROW subgroups.
- A linear regression will be conducted, with change in SBP from baseline to 6 months as measured by 24-hour ABPM as the dependent variable, and baseline systolic ABPM, treatment, NA/ROW, treatment * NA/ROW interaction term as independent variables. If the interaction term is not significant at 0.15 level, then the treatment effect in the primary effectiveness endpoint is considered consistent between NA and ROW subgroups.

9.4. Handling of Missing Data and Dropouts

Every effort will be made to minimize missing data for the primary efficacy endpoint. A secondary analysis will be performed where missing data is imputed using SAS PROC MI. Missing 6-month outcomes will be imputed using baseline SBP, 3-month SBP, treatment group, age, gender and BMI. One hundred

imputed datasets will be generated using a MCMC (Markov Chain Monte Carlo) algorithm, and a pooled estimate of the treatment effect will be generated using SAS PROC MIANALYZE.

9.5. Adjustments for Multiple Comparisons

The primary safety and efficacy endpoints are independently powered and no adjustments for multiple comparisons will be made.

9.6. Demographic and Other Baseline Characteristics

Baseline variables will be tabulated. Categorical variables, including binary variables, will be reported by giving the number and percentage of patients in each category. Continuous variables will be reported by presenting the number of values, mean, standard deviation, median, minimum, and maximum value for each. No imputation will be performed for missing data unless otherwise stated.

9.7. Treatment Characteristics

Renal denervation treatment measures such as number of ablation attempts and number of generator codes will be summarized separately for each kidney, and for combined kidneys. Anti-hypertensive medication use will also be summarized at baseline and at each follow-up.

9.8. Interim Analyses

Interim analyses will be conducted and reviewed by the DSMB, along with an independent organization that will be performing the Bayesian analyses. Medtronic personnel will not have access to any unblinded results prior to the primary endpoint analyses. The interim analyses will take place when a minimum of N=110 and N=149 subjects have evaluable 6-month efficacy data, with a maximum study size of N=260 randomized subjects if the study does not stop at an interim look. With an expected attrition rate of 15% at 6-months, this will require approximately N=130 and N=175 randomized subjects at the first and second interim analyses.

1. The first interim analysis takes place when a minimum of 110 subjects have evaluable 6-month efficacy data, requiring approximately 130 randomized subjects to account for 15% attrition. If the attrition rate is higher than 15%, then additional subjects will be randomized in order to reach a minimum of 110 evaluable. The Bayesian efficacy analysis will be performed and $P[\text{suc}]$ will be calculated, where $P[\text{suc}]$ is the probability of accepting the alternative efficacy endpoint hypothesis, $P(\mu < 0 | y, y_0, \hat{\theta}(y, y_0, \lambda, k))$, and is defined in detail in section 9.9.3.
 - a. If $P[\text{suc}] > 0.975$ then the study has met the efficacy hypothesis and enrollment will be stopped. Any additional subjects that have been enrolled before the decision is made to stop for efficacy will be pooled with the existing subjects and analyzed as a secondary cohort.
 - b. We calculate the probability of futility based on the maximum study size of 260 randomized subjects which requires us to impute the outcomes for subjects who have not yet been enrolled (see sections 9.8.2 and 9.8.3 below for details). If the posterior probability of futility from this calculation is < 0.05 for the primary efficacy endpoint, then the study will have met the futility boundary and enrollment will be stopped. Any

- additional subjects that have been enrolled before the decision is made to stop for futility will be pooled with the existing subjects and analyzed as a secondary cohort.
- c. If the stopping rules in a and b above are not met, then we continue enrolling subjects to the second interim analysis.
2. If we don't stop for efficacy or futility at the first interim analysis, then enrollment will continue until the second interim analysis when a minimum of 149 subjects have evaluable 6-month efficacy data, requiring 175 randomized subjects to account for attrition. If the attrition rate is higher than 15%, then additional subjects will be randomized in order to reach a minimum of 149 evaluable. The Bayesian efficacy analysis will be performed and P[suc] will be calculated.
 - a. If $P[\text{suc}] > 0.975$ then the study has met the efficacy hypothesis and enrollment will be stopped. Any additional subjects that have been enrolled before the decision is made to stop for efficacy will be pooled with the existing subjects and analyzed as a secondary cohort.
 - b. We calculate the probability of futility based on the maximum study size of 260 randomized subjects which requires us to impute the outcomes for subjects who have not yet been enrolled (see sections 9.8.2 and 9.8.3 below for details). If the posterior probability of futility from this calculation is < 0.05 for the primary efficacy endpoint, then the study will have met the futility boundary and enrollment will be stopped. Any additional subjects that have been enrolled before the decision is made to stop for futility will be pooled with the existing subjects and analyzed as a secondary cohort.
 - c. If the stopping rules in a and b above are not met, then we continue enrolling subjects to the final analysis.
 3. If we don't stop for efficacy or futility at the second interim analysis, then enrollment will continue until the maximum study size of 260 randomized subjects. This will result in 221 evaluable subjects based on a 15% attrition rate. The Bayesian efficacy analysis will be performed and P[suc] will be calculated for the primary efficacy endpoint.
 - a. If $P[\text{suc}] > 0.975$ then we have met the primary efficacy endpoint hypothesis.

9.8.1. Mathematical forms for success:

$$P(\mu < 0 | y, y_0, \hat{\alpha}(y, y_0, \lambda, k)) > 0.975$$

where y and y_0 represent the prospective data and prior data respectively, the notation $\hat{\alpha}(y, y_0, \lambda, k)$ is used to denote that the estimate of the discounting parameter $\hat{\alpha}$, which depends on the prospective data, prior data, and the Weibull shape and scale parameters, and $\mu = \mu_t - \mu_c$ represents the baseline-adjusted treatment effect of BP change comparing RDN and control groups. See section 9.9.3 for more details.

9.8.2. Mathematical forms for futility:

$$\frac{\sum_1^{N_{rep}} I(P(\mu < 0 | y_{imp}) > 0.975)}{N_{rep}} < 0.05$$

Where y_{imp} is a single complete dataset after imputation, N_{rep} is the number of imputation simulations done and $\mu = \mu_t - \mu_c$ represents the baseline-adjusted treatment effect of BP change comparing RDN and control groups where μ_t and μ_c are the baseline adjusted BP changes in the RDN and control groups respectively.

9.8.3. Futility imputation procedure

For the futility calculation, we calculate the probability of futility based on the maximum study size of 260 randomized subjects which means we have three types of subjects to consider:

1. Subjects who have reached their 6-month endpoint.
2. Subjects who are enrolled and have baseline blood pressure but have not reached their 6 month endpoint.
3. Subjects who have not been enrolled.

Imputation procedures will be used to impute the blood pressure change for subjects of type 2 and type 3 above.

For type 2 subjects we use the following procedure:

- 2.1 Construct the posterior predictive distribution for blood pressure change using type 1 subjects, incorporating the prior data.
- 2.2 Simulate samples from the predictive distribution to impute the missing values of blood pressure change for type 2 subjects, conditional on observed baseline blood pressure.

For type 3 subjects, we do the following:

- 3.1 Construct the posterior predictive distribution for blood pressure change using type 1 subjects, including the prior data.
- 3.2 Simulate baseline blood pressure for type 3 patients.
- 3.3 Simulate blood pressure change from the predictive distribution.
- 3.4 Impute blood pressure change for type 3 subjects, conditional on simulated baseline blood pressure.

We then combine the type 1 subjects with the imputed subjects from steps 2.2 and 3.4 into a single dataset and construct the endpoint using the BayesDP function. This procedure will be repeated for many datasets ($N_{rep} = 1000$) and we calculate the number of times the alternative hypothesis is accepted. If the proportion of times the alternative hypothesis is accepted is less than 5%, stop enrollment due to futility.

We will use v1.3.2. of the bayesDP package, available on the Comprehensive R Archive Network (CRAN) [<https://CRAN.R-project.org/>].

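### The futility calculation in SAP 9.8.3 has no attrition step, so it predicts success on about 240 or 234 outcomes when the SAP expects 221, and modestly overstates that probability near the 5% boundary

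*SAP*

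**What the plan says.** SAP 9.8.3 sets the horizon of the futility calculation: "we calculate the probability of futility based on the maximum study size of 260 randomized subjects". It sorts subjects into three types: those who have reached the 6-month endpoint (type 1), those enrolled with a baseline value who have not reached it (type 2), and those not yet enrolled (type 3). It then states: "Imputation procedures will be used to impute the blood pressure change for subjects of type 2 and type 3 above". The completed dataset is formed without any loss: "We then combine the type 1 subjects with the imputed subjects from steps 2.2 and 3.4 into a single dataset". The success test is run on 1,000 such datasets, with this rule: "If the proportion of times the alternative hypothesis is accepted is less than 5%, stop enrollment due to futility".

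Elsewhere the SAP counts attrition. For the maximum of 260 randomized, 9.8 says: "This will result in 221 evaluable subjects based on a 15% attrition rate". The looks are sized the same way, the first "requiring approximately 130 randomized subjects to account for 15% attrition" and the second "requiring 175 randomized subjects to account for attrition". Section 8 and Table 4 repeat 221 evaluable from 260 randomized, and Table 3 lists 15% attrition as a simulation parameter. Section 9.4 makes imputation of missing 6-month outcomes a secondary analysis only.

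**The concern.** A predictive probability should describe the test that will actually be carried out. The primary test is expected to run on about 221 evaluable subjects, because multiple imputation is not part of it. The written procedure describes a larger test. When the interim result is weak, more future outcomes give more room for recovery, so the predictive probability rises and the 5% rule triggers less often.

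Section 9.8.3 also does not place subjects who have already dropped out. Such a subject is enrolled, has a baseline value and has not reached the 6-month endpoint, so the wording allows type 2.

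What is at stake is the efficiency of the futility rule: a trial of an ineffective device would run on somewhat more often than the 221-subject plan implies.

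**Working it through.** **Inputs.** From 9.8: 110 evaluable of about 130 randomized at look 1, 149 of 175 at look 2, 260 randomized at most, 15% attrition, futility below 5%, success above 0.975. From Table 3: SD 12; prospective means -6.8 and -1.8 mmHg; prior means -8.85 and -1.80 mmHg, each with SE 1.75. From 9.9.4.1: Weibull shape 3, scale 0.25. From section 8: allocation 1:1 for subjects 81 to 106, then 2:1.

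**The SAP's own counts.** 260 × 0.85 = 221; 130 × 0.85 = 110.5; 175 × 0.85 = 148.75. These agree with the stated 221, 110 and 149.

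**Size of the completed dataset.**

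| | With 15% attrition | As written | Dropouts also imputed |
|---|---|---|---|
| Look 1 | 110 + 0.85 × 130 = 220.5 | 110 + 130 = 240 | 260 |
| Look 2 | 149 + 0.85 × 85 = 221.25 | 149 + 85 = 234 | 260 |

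The analyzed dataset is therefore 240/221, or 8.6%, too large at look 1 and 234/221, or 5.9%, too large at look 2.

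**Effect at the boundary (flat prior, known variance).** With interim statistic z on n subjects and final size N, the predictive probability is Φ[(√N·z − 1.96·√n)/√(N − n)].

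- Look 1, n = 110. Setting the value at N = 221 to 5% gives z = (1.96 × 10.488 − 1.645 × 10.536)/14.866 = 0.217. At N = 240: Φ[(15.492 × 0.217 − 20.557)/11.402] = Φ(−1.51) = 6.6%. At N = 260: Φ(−1.39) = 8.2%.
- Look 2, n = 149. z = (1.96 × 12.207 − 1.645 × 8.485)/14.866 = 0.670. At N = 234: Φ[(15.297 × 0.670 − 23.925)/9.220] = Φ(−1.48) = 6.9%. At N = 260: Φ(−1.24) = 10.7%.

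Using the expected arm sizes, the observed difference at which the rule triggers moves from -0.57 to -0.34 mmHg at look 1 and from -1.41 to -1.22 mmHg at look 2 on the written rule.

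**Simulation with the discounted prior.** This approximates the 9.9.4.1 model: normal posterior, SD 12 treated as known, no explicit baseline covariate, evaluable arms of 70/40, 96/53 and 144/77, discount 1 − exp(−(p/0.25)³), and 1,000 predictive replicates per look.

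With 40,000 trials under the alternative and a 221 target, power is 96.0% (Table 4: 96%), 82.2% at look 1 (83%) and 90.6% cumulatively at look 2 (91%).

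| | 221 | 240/234 | 260 |
|---|---|---|---|
| Futility stops, alternative | 1.63% | 1.34% | 1.09% |
| Power | 96.0% | 96.1% | 96.2% |
| Futility stops, no effect (both arms -1.8; 8,000 trials) | 81.1% | 78.7% | 74.0% |
| Type I error, same scenario | 0.0436 | 0.0439 | 0.0440 |

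Under no effect the loss is 81.1 − 78.7 = 2.4 points, or 81.1 − 74.0 = 7.1 points if dropouts are imputed.

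**Which rule produced Table 4.** The stated 1.71% from 8,000 trials has a Monte Carlo standard error of √(0.0171 × 0.9829/8000) = 0.14 points. The 221 target (1.63%) lies well within that; the written rule (1.34%) is 0.37 points away.

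**The case against.** The best defence is that the SAP ties 260 randomized to 221 evaluable so often (section 8, 9.8, Table 4) that 9.8.3 must mean 221. The simulated futility rate supports this. The argument stands for how Table 4 was probably produced, but it does not supply the missing step: 9.8.3 tells the independent organization to impute every type 2 and type 3 subject.

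It can also be said that the effect is small, that it errs towards preserving power, and that the SAP sets no target for futility stopping under no effect. All three are true, and they limit the weight of the point. So does a worked example: at an observed difference of -0.5 mmHg at look 1, the discounted-prior predictive probability is 2.9% at 221 and 4.1% at 240, so the trial stops either way. Only at 260 (5.4%) does it continue.

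A reader might also infer from 9.8.2 that futility is judged without the prior data, because the formula conditions only on a term that "is a single complete dataset after imputation", whereas 9.8.1 also lists the prior data and the discount. The SAP does not support that reading. Section 9.8.3 includes the prior data when it builds the predictive distribution, and it constructs each endpoint with the BayesDP function. The difference is one of notation.

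**Conclusion.** The point holds as a modest specification flaw that should be corrected. As written, 9.8.3 evaluates futility for about 240 outcomes at look 1 and 234 at look 2, while the SAP's final analysis has about 221. Near the boundary the predictive probability rises from 5.0% to 6.6% or 6.9%, and futility stopping under no effect falls by about 2 to 3 points. The 7-point loss applies only if known dropouts are also imputed, which the text permits but does not state.

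Two stronger readings are not supported. The efficacy conclusion is not threatened, since simulated power moves by 0.2 points at most and type I error is practically unchanged. Nor is the 1.71% in Table 4 shown to be wrong, since it fits the 221-subject rule.

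The counts follow directly from the SAP, and the boundary figures need only a flat prior and known variance. The stopping rates rest on the approximate simulation. It matches Table 4's power only with 0.25 used as a Weibull scale (the formula as printed gives about 86%). It gives a type I error of 0.0436, against the stated 0.038, under a null scenario that the SAP does not specify. The overstatement is also confined to the range that matters for futility: at look 2, once the predictive probability exceeds about 90%, it vanishes or slightly reverses.

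**What to change.** In 9.8.3, apply the 15% attrition rate, or the rate observed to date, to type 2 and type 3 subjects (for example by drawing a dropout indicator for each), so that the completed dataset targets about 221 evaluable subjects at either look. State that subjects already known to have dropped out are not imputed.

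Confirm that the 1.71% in Table 4 was produced under that rule, and re-run it only if it was not. The conditioning in 9.8.2 can be aligned with 9.8.1 at the same time, as an editorial change.

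The cost is a few lines of text and a small change to the futility code, plus one simulation run if the literal rule was used. The maximum size, the looks and the success criterion stay as they are.
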